The protocol, informed consent form(s), recruitment materials, and all participant materials will be submitted to the Institutional Review Board (IRB) for review and approval. Approval of both the protocol and the consent form must be obtained before any participant is enrolled. Any amendment to the protocol will require review and approval by the IRB before the changes are implemented to the study. In addition, all changes to the consent form will be IRB-approved; a determination will be made regarding whether a new consent needs to be obtained from participants who provided consent, using a previously approved consent form.

Glossary of Abbreviations

AE	Adverse event
ALT (SGPT)	Alanine transaminase (serum glutamate pyruvic transaminase)
AML	Acute myeloid leukemia
ANC	Absolute neutrophil count
AST (SGOT)	Aspartate transaminase (serum glutamic oxaloacetic transaminase)
B-HCG	Beta human chorionic gonadotropin
BMT	Bone marrow transplant
CBC	Complete blood count
CFR	Code of Federal Regulations
CNS	Central nervous system
CR	Complete response
CRc	Cytogenetic complete remission
CRi	Complete remission incomplete
CRm	Morphologic complete remission
CRF	Case report form
CST	Central standard time
CT	Computed tomography
CTCAE	Common Terminology Criteria for Adverse Events
CTEP	Cancer Therapy Evaluation Program
DLT	Dose limiting toxicity
DNA	deoxyribonucleic acid
DSM	Data and Safety Monitoring
DSMC	Data Safety Monitoring Committee
ECG (or EKG)	Electrocardiogram
ECOG	Eastern Cooperative Oncology Group
EDTA	ethylenediaminetetraacetic acid
FDA	Food and Drug Administration
FISH	fluorescent in situ hybridization
FWA	Federal wide assurance
GCP	Good Clinical Practice
HHS	Department of Health and Human Services
HIV	Human Immunodeficiency Virus
HRPO	Human Research Protection Office (IRB)
IND	Investigational New Drug
IRB	Institutional Review Board
MDS	Myelodysplastic syndrome
MM	Multiple myeloma
MRI	Magnetic resonance imaging
MTD	Maximum tolerated dose
NCCN	National Cancer Center Network

NCI	National Cancer Institute
NIH	National Institutes of Health
NSCLC	Non-small cell lung cancer
OHRP	Office of Human Research Protections
ORR	Overall response rate
OS	Overall survival
PBMC	Peripheral blood mononuclear cell
PD	Progressive disease
PI	Principal investigator
PR	Partial response
PSA	Prostate-specific antigen
QASMC	Quality Assurance and Safety Monitoring Committee
RECIST	Response Evaluation Criteria in Solid Tumors (Committee)
RFS	Relapse free survival
RR	Response rate

	APPENDIX C: PATIENT'S MEDICATION DIARY	49
	APPENDIX D: Definitions for Adverse Event Reporting	50
	APPENDIX E: Reporting Timelines	53
	APPENDIX F: Symptom Assessment Form	56

PROTOCOL SUMMARY

Synopsis

Title:	Fostamatinib as a single agent or in combination with ruxolitinib for treatment of patients with myelofibrosis with severe thrombocytopenia
Study Description:	
Our hypothesis is that fostamatinib will be safe, tolerable, and effective in patients with myelofibrosis with severe thrombocytopenia (platelet < 50K/microL) as a single agent and in combination with ruxolitinib. Fostamatinib will improve thrombocytopenia in patients with myelofibrosis (MF) with severe thrombocytopenia (platelet < 50K/microL) and allow them to initiate treatment with ruxolitinib.
 
This study will be executed in two parts (Part A and Part B). For Part A, patients with MF with severe thrombocytopenia will initially receive 12 weeks of single agent fostamatinib (by mouth twice daily) until a sustained platelet count of ≥ 50K/microL is achieved (defined as two separate measurements at least two weeks apart).
 
Patients who achieve a sustained platelet count of ≥ 50K/microL will be eligible to continue on to Part B where they will begin treatment with ruxolitinib (dosed as per standard of care) while continuing to take fostamatinib. Patients who do not achieve a sustained platelet count of ≥ 50K/microL by the end of 12 weeks of treatment may continue on fostamatinib monotherapy if they are receiving benefit for up to an additional 36 weeks of treatment, and may be eligible to continue on to Part B of the study if they achieve a sustained platelet count of ≥ 50K/microL at any point before Cycle 10 Day 1.
 
Patients in Part B will continue treatment with fostamatinib and ruxolitinib for up to an additional 36 weeks (total duration of treatment with fostamatinib monotherapy and fostamatinib and ruxolitinib combination therapy will be 48 weeks).

Objectives:	
Part A:
 
Primary Objective: Evaluate the impact of fostamatinib on platelet counts in patients with myelofibrosis and severe thrombocytopenia (platelets < 50K/microL)
 
Secondary Objectives:
 
 Evaluate the safety and tolerability of single agent fostamatinib in patients with MF and thrombocytopenia Evaluate spleen response to fostamatinib

	
 3. Evaluate anemia response to fostamatinib 4. Evaluate the impact of fostamatinib on transfusion requirements 5. Evaluate the impact of fostamatinib on MF symptoms 6. Evaluate the ability of fostamatinib treatment to enable initiation with ruxolitinib 7. Evaluate the impact of fostamatinib on marrow fibrosis 
Part B:
 
Primary Objective: Evaluate the safety and tolerability of fostamatinib plus ruxolitinib in patients with MF and thrombocytopenia
 
Secondary Objectives:
 
 1. Evaluate spleen response with the combination of fostamatinib and ruxolitinib 2. Evaluate the impact of fostamatinib and ruxolitinib on symptoms 3. Evaluate the ability of fostamatinib to enable sustained treatment with ruxolitinib 4. Evaluate the impact of fostamatinib and ruxolitinib on marrow fibrosis
Endpoints:	
Part A:
 
Primary Endpoint: Platelet response as defined as an increase in platelet count $\geq 50K/\text{microL}$ with at least one more confirmatory platelet count separated by at least 2 weeks (in the absence of platelet transfusion) within the first 12 weeks of fostamatinib treatment
 
Secondary Endpoints:
 
 1. Platelet response by week 12 and at end of fostamatinib monotherapy treatment 2. Number of patients eligible to initiate therapy with ruxolitinib 3. Adverse events (AEs), serious AEs (SAEs), and laboratory abnormalities on fostamatinib treatment 4. Patients who permanently discontinued fostamatinib due to fostamatinib related AEs 5. Patients who required treatment interruption of fostamatinib due to AEs 6. Patients who were dose escalated who tolerated fostamatinib dose greater than 100 mg BID 7. Patients who achieve 35% or greater reduction in spleen volume as determined by ultrasound at week 12 of fostamatinib treatment and end of fostamatinib monotherapy treatment

	
 8. Mean reduction in spleen volume as determined by ultrasound at week 12 of fostamatinib treatment and end of fostamatinib monotherapy treatment 9. Patients with 50% or greater improvement in Total Symptom Score at week 12 of treatment and end of fostamatinib monotherapy treatment 10. Patients who achieve platelet transfusion independence 11. Patients with anemia who achieve RBC transfusion independence 12. Change in marrow fibrosis by WHO grading
	
Part B:
 
Primary Endpoint: Incidence, severity, and outcomes of AEs per NCI CTCAE v 5.0, SAEs, AEs of interest (AEIs) and laboratory abnormalities during fostamatinib and ruxolitinib treatment

	
Secondary Endpoints:
 
 1. Patients with 35% or greater reduction in spleen volume as determined by ultrasound after 12 weeks of combination therapy and end of treatment 2. Mean reduction in spleen volume as determined by ultrasound after 12 weeks of combination therapy and end of treatment 3. Patients with a 50% or greater improvement in Total Symptom Score after 12 weeks of combination therapy and at end of treatment 4. Duration of uninterrupted ruxolitinib treatment 5. Change in marrow fibrosis by WHO grading
Study Population:	Twelve adult patients of any race or ethnicity with primary or secondary myelofibrosis with severe thrombocytopenia (platelet count < 50K/microL) with intermediate or high risk disease by IPSS.
Phase:	Pilot Phase II Study
Description of Sites / Facilities Enrolling:	This study will be active at Washington University School of Medicine.
Description of Study Intervention:	Both fostamatinib and ruxolitinib are oral drugs taken twice daily on a continuous basis.
Study Duration:	2 years
Participant Duration:	48 weeks

STUDY SCHEMA

[figure not shown]
Part A:

The starting dose of fostamatinib is 100 mg twice daily (BID). After the first cycle, if no major dose related safety issue is observed and the platelet count is less than 50K/microL, then the fostamatinib dose will be increased to 150 mg BID for the next 2 cycles; otherwise the dose may be continued at 100 mg BID.

Part B:

After 3 cycles of fostamatinib monotherapy, all patients with a sustained platelet count \geq 50K/microL, will continue on the current fostamatinib dose plus ruxolitinib at the recommended dose per standard prescribing guidelines for an additional 9 cycles.

Patients who do not reach platelet count of at least 50K/microL but who achieve clinical benefit per the treating provider may continue on single agent fostamatinib for up to 12 total treatment cycles. If these patients achieve a sustained platelet count of \geq 50K/microL at any point prior to Cycle 10 Day 1, then they may be eligible to enroll in Part B of the study and continue treatment with fostamatinib and ruxolitinib for the remainder of the study.

SCHEDULE OF ACTIVITIES

	Screening ¹	D1 of each cycle ²	D15 of each cycle	EOT Part A	C4D1	After 3 cycles Part B	EOT Part B	Follow-up ³
Informed consent	X							
H&P, ECOG PS, con med	X	X						
Medical history	X							
CBC	X	X ⁴	X ⁴					
Select chemistry ⁵	X	X	X					
PT/INR, PTT	X							
Lipid Panel ⁶	X	X ⁶						
Pregnancy test ⁷	X	X						
ECG	X							
Abdominal ultrasound for spleen volume ⁸	X			X	X	X	X	
Bone marrow biopsy	X ⁹			X ⁸			X ⁸	
MPN symptom assessment form		X						
Fostamatinib		Oral drug taken on a twice daily basis						
Ruxolitinib		As per SOC						
AE assessment		Start of treatment through 30 days after last day of study treatment						
Progression and survival								X

1. Screening evaluations must be conducted within 3 weeks prior to the start of therapy.
2. Each cycle is 28 days. +/- 3 day for Day 1 assessments
3. Every 6 months for up to 2 years.
4. Also on D8 and D22 (weekly) the first cycle of fostamatinib monotherapy and first cycle of fostamatinib + ruxolitinib combination therapy (+/- 2 days)
5. BUN, creatinine, total bilirubin, AST, ALT, albumin
6. Total Cholesterol, LDL, HDL, non-HDL, Triglycerides, check every 2 cycles after starting ruxolitinib therapy
7. Women of childbearing potential only; test may be a urine test, and if positive, confirm with a serum test.
8. +/- 7 days
9. May be done up to 30 months before signing consent

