5.3 Study Intervention Administration

In Part A of the study, patients will initially receive fostamatinib single agent at a starting dose of 100 mg PO twice daily (BID) for three cycles (12 weeks). Each cycle is 28 days (4 weeks).

Patients who tolerate single agent fostamatinib and achieve a sustained platelet count of $\geq 50,000/\text{microL}$ on at least two separate measurements taken at least two weeks apart at any point before Cycle 10 Day 1 will be eligible to proceed to Part B of the study and initiate treatment with ruxolitinib (starting dose will be determined by platelet count as per package insert).

For patients who do not achieve a sustained platelet count of $\geq 50,000/\text{microL}$ following the first cycle (4 weeks) of fostamatinib 100 mg BID and no AEIs (see Section 5.5) are reported, then the dose of fostamatinib may be increased to 150 mg BID and continued for subsequent cycles. If a platelet count of $\geq 50,000/\text{microL}$ is not achieved after three cycles of fostamatinib, but the patient is achieving clinical benefit, then the patient may continue on fostamatinib monotherapy for up to a total of 12 cycles of treatment and may continue

on to Part B of the study if they achieve a sustained platelet count of $\geq 50,000/\text{microL}$ by Cycle 10 Day 1. If the patient is not achieving clinical benefit or has evidence of disease progression, then the patient will be taken off study.

For Part B of the study, patients will continue on treatment with fostamatinib for up to an additional nine cycles (36 weeks) to complete a total treatment duration of 48 weeks. Ruxolitinib will be initiated in combination with fostamatinib at the start of Part B unless the patient is experiencing progressive MF symptoms and is eligible to initiate ruxolitinib, in which case ruxolitinib may be initiated sooner at the discretion of the PI. If the platelet count decreases to $< 50,000/\text{microL}$ following initiation of ruxolitinib, then the dose of fostamatinib may be increased to 150 mg BID if the patient is on the 100 mg BID dose.

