12.2 Study Design

This is a hypothesis generating limited pilot phase II study evaluating the efficacy and safety of the use of fostamatinib as a single agent and when given in combination with ruxolitinib in patients with intermediate to high risk myelofibrosis. Previous studies with fostamatinib and ruxolitinib monotherapy indicate that toxicity will be low grade and reversible with standard treatment.

This study consists of two parts. For Part A, patients with MF and severe thrombocytopenia will initially receive 12 weeks of single agent fostamatinib and the primary endpoint will be platelet response (defined as platelet count of $\geq 50K/\text{microL}$ as two separate measurements at least two weeks apart) at the end of the 12 week treatment period. Patients who achieve a sustained platelet response will then be eligible to proceed to Part B of the study and begin treatment with ruxolitinib while continuing to take fostamatinib. For Part B, patients will continue treatment with fostamatinib and ruxolitinib for up to an additional 36 weeks and the primary endpoint will be safety as assessed by NCI CTCAE v 5.0. Patients who do not have a sustained platelet response after 12 weeks of treatment but are clinically benefiting from fostamatinib may remain on Part A of the study and be eligible to enroll in Part B if they achieve a sustained platelet response prior to Day 1 Cycle 10 of treatment.

A maximum of 12 patients will be enrolled. A Bayesian sequential monitoring rule will be implemented for safety.

Safety monitoring (Part B): The stopping rule is defined as $\text{Pr}(\theta > \theta_T | \text{data}) > 0.8$, where θ denotes the proportion of AEs of interest as defined in Section 5.5 and θ_T denotes the rate of AEs of interest under the null hypotheses (i.e., 20% AEs of interest). That is, an early termination of the study due to excessive toxicities will be recommended whenever, given the accumulated observed data, there is high chance (i.e., >80% probability) for the “true” AEs of interest rate >20%. The stopping boundaries were obtained using Multc99 version 2.1, a free-download software from M.D. Anderson Cancer Center. Specifically, we assume that the parameter θ follows a prior distribution of beta (0.2, 0.8), i.e., θ with mean = 0.2 but with relatively large variability (non-informative prior). Early stopping will be recommended if we observe 3 patients who experience AEs of interest out of first 5 patients

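### The start of ruxolitinib for a patient whose platelet response is sustained before week 12 is not stated consistently, so some Part A week-12 readings could be taken on both drugs

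*Combined protocol and SAP*

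**What the plan says.** Four places bear on the start of ruxolitinib.

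- **Synopsis, Study Description.** Part A patients "will initially receive 12 weeks of single agent fostamatinib (by mouth twice daily) until a sustained platelet count of" at least 50K/microL. Part B then adds up to 36 weeks, and the "total duration of treatment with fostamatinib monotherapy and fostamatinib and ruxolitinib combination therapy will be 48 weeks".
- **Study Schema, Part B.** "After 3 cycles of fostamatinib monotherapy, all patients with a sustained platelet count" at or above the threshold go on to fostamatinib plus ruxolitinib for nine more cycles.
- **Section 5.3.** Monotherapy is given for three cycles. Patients with a sustained count "at any point before Cycle 10 Day 1 will be eligible to proceed to Part B of the study and initiate treatment with ruxolitinib". Ruxolitinib begins when Part B begins, except that an eligible patient with progressive myelofibrosis symptoms may begin it earlier if the PI so decides.
- **Section 12.2.** Patients "will initially receive 12 weeks of single agent fostamatinib and the primary endpoint will be platelet response", read at the close of the 12 weeks. Responders are then eligible for Part B.

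The late limit on entry to Part B also varies. The synopsis, schema, 12.2 and one sentence of 5.3 require the sustained count before Cycle 10 Day 1. A later sentence of 5.3 says "by Cycle 10 Day 1".

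**The concern.** For a patient confirmed early, the end of 12 weeks and the attainment of a sustained count are different dates, and the synopsis names both. The schema settles the matter one way. Section 5.3 leaves the earliest date open and adds an exception that the schema and 12.2 do not carry.

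What is at stake is the interpretation of Part A as a single-agent evaluation. The synopsis lists spleen and symptom endpoints for Part A at week 12 of fostamatinib. Section 1.2 says ruxolitinib reduces spleen size and improves symptoms, so a week-12 value taken after ruxolitinib has begun could credit its effect to fostamatinib. Section 1.3 says ruxolitinib can lower platelets, so a response read at the end of 12 weeks, as 12.2 words it, could be lost for the opposite reason. The Part A adverse event endpoint covers events on fostamatinib treatment without limiting it to monotherapy, and 12.3 has no rule assigning events to a part.

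**Working it through.** **Inputs.** Cycle length is 28 days. CBCs fall on Days 1, 8, 15 and 22 of Cycle 1, then on Days 1 and 15 (Schedule of Activities). A sustained count is two counts at least two weeks apart (Section 10.2.2). Part B lasts up to nine cycles and total treatment is 48 weeks (synopsis, 5.3).

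**The plan's own duration.** 3 × 28 days = 84 days = 12 weeks. 9 × 28 days = 252 days = 36 weeks. 12 + 36 = 48 weeks, as stated.

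**Earliest confirmation.** Among scheduled post-dose CBCs at nominal days, the first pair at least 14 days apart is C1D8 and C1D22. Confirmation is therefore possible on day 22, three weeks after the first dose. The next Day 1 visit is C2D1, day 29, at four weeks.

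**Durations under different starts of combination therapy.**

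| Start | 36 weeks of Part B ends at | Combination needed to reach week 48 | Ruxolitinib before week 12 |
|---|---|---|---|
| Week 3 (day 22) | 3 + 36 = 39 | 48 − 3 = 45 | 12 − 3 = 9 weeks |
| Week 4 (C2D1) | 4 + 36 = 40 | 48 − 4 = 44 | 12 − 4 = 8 weeks |
| Week 12 (C4D1) | 12 + 36 = 48 | 48 − 12 = 36 | 0 |

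For a patient who completes treatment, only the week-12 start satisfies both the 36-week limit on Part B and the 48-week total. The weeks 3 and 4 rows are the earliest cases that the CBC schedule permits; neither start date is stated anywhere in the documents.

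**Effect on each endpoint.**

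- Synopsis primary endpoint: a confirmed response at any time in the first 12 weeks. Eligibility for Part B requires the same confirmation, so an early responder has met it before taking ruxolitinib.
- Section 12.2 wording of that endpoint: read at the end of 12 weeks, so it can fall on both drugs.
- Part A spleen and symptom endpoints at week 12: the C4D1 ultrasound and symptom form can fall on both drugs.
- The same endpoints at the end of monotherapy: not affected, provided the reading precedes ruxolitinib.
- Part B adverse events: the synopsis already defines these by exposure to both drugs. The Part A count has no matching cut-off.

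**Weight of one patient.** With all 12 evaluable, one patient moves a reported rate by 1/12 = 8.3 percentage points and two by 2/12 = 16.7.

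**The case against.** The strongest reply is that the plan does have a rule and one synopsis sentence is badly worded. The schema is explicit for all sustained responders, and 12.2 agrees. The synopsis and 5.3 both state 12 weeks as well. The clause in 5.3 on Cycle 10 sets eligibility and a late limit, which is not a start date. The exception points the same way: an early start of ruxolitinib has meaning only if Part B normally begins after the patient becomes eligible. The durations close only at 12 weeks. The study is also a 12-patient descriptive pilot.

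Most of this stands. A reader might infer that the synopsis and 5.3 set a start-on-confirmation rule opposed to the schema and 12.2. The text does not support that clean split, because the synopsis and 5.3 are ambiguous within themselves. A reader might also infer that early responders get 44 weeks of combination therapy, but that exceeds the 36-week limit on Part B.

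The reply does not remove the exception in 5.3. On its own terms it permits ruxolitinib before Part B, and neither the schema nor the analysis section allows for it. So even if the normal start is taken as settled at 12 weeks, Part A week-12 readings can still be taken on both drugs, and nothing in 12.3 says how to handle them.

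**Conclusion.** The point holds in limited form. The four places do not agree on when ruxolitinib may start for a patient with a sustained count before week 12. In the worst case about 8 to 9 weeks of ruxolitinib could precede the week-12 readings.

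The affected items are the 12.2 wording of the primary endpoint, the Part A week-12 spleen and symptom endpoints, and the Part A adverse event counts. A reader might infer that the primary endpoint itself is compromised. As the synopsis times it, it is not. This assumes that the endpoint means reaching 50K/microL, as 10.2.2 and 12.2 have it, and that eligibility in the 5.3 exception means the sustained count.

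A reader might also take the 20% and 40% response rates in 12.4 to mean that 2.4 to 4.8 of 12 patients are affected. Those are illustrative overall rates, and nothing gives the share confirmed early. The number affected cannot be derived and is at most the number of early responders.

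The difference between before and by Cycle 10 Day 1 matters only for a count completed on that day, which is a scheduled CBC visit. Overall severity is minor to moderate.

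**What to change.** 1. The sponsor should reconcile the synopsis, the schema, 5.3 and 12.2 on when Part B and ruxolitinib start, including whether the 5.3 exception applies and where it is stated. The late limit at Cycle 10 Day 1 should read the same throughout. Which rule is right is for the sponsor to state.
2. Word the primary endpoint in 12.2 as the synopsis does, as a confirmed response during the first 12 weeks of fostamatinib.
3. Add to 12.3 that adverse events and efficacy readings are assigned to Part A or Part B by the date of the first ruxolitinib dose. For a patient who starts ruxolitinib before week 12, the Part A spleen and symptom result is then the end-of-monotherapy reading, from the EOT Part A ultrasound and the Day 1 symptom form already scheduled.

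The cost is wording in four places and one sentence in 12.3. The drawback is that Part A readings for these patients come before week 12. If ruxolitinib began between Day 1 visits, the last symptom form before it would be used; for a start before C2D1 that would be the C1D1 form, so no change from baseline could be measured.

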1.0 INTRODUCTION

1.1 Background

Myelofibrosis (MF) is a clonal stem cell disorder classified within the category of Philadelphia chromosome (Ph)-negative myeloproliferative neoplasms (MPN) that includes polycythemia vera (PV) and essential thrombocythemia (ET) [1]. The disease is characterized by ineffective erythropoiesis and extramedullary hematopoiesis leading to progressive bone marrow failure, severe anemia, constitutional symptoms (e.g., night sweats, fever, fatigue), marked hepatosplenomegaly, thrombosis, and cachexia. MF can arise following a history of PV or ET or can present *de novo* as primary myelofibrosis (PMF).

Among the Ph-negative MPNs, somatic mutations in Janus kinase 2 (JAK2) constitute the most frequent mutation in PV, ET, and PMF [2]. Approximately 50 – 60% of patients with PMF harbor the JAK2 V617F mutation. Mutations in calreticulin (CALR) and myeloproliferative leukemia virus oncogene (MPL) have subsequently been identified in patients with ET and PMF who are negative for the JAK2 mutation [3- 7]. Patients with CALR mutation appear to have a more indolent clinical course than patients with the JAK2 V617F mutation as manifested by lower risk of thrombosis and longer overall survival [3- 4]. Several additional molecular mutations have been identified in patients with MF that have also shown to have prognostic impact [8-9]. Mutations in ASXL1, SRSF2, and IDH1/IDH2, for example, are associated with increased risk for leukemic transformation and decreased overall survival.

MF generally affects an older population, with the age at diagnosis around 65 years of age [10]. Median survival can range from months to years depending on the presence or absence of adverse clinical and molecular prognostic factors [11-13], but ultimately survival is significantly reduced in patients with MF compared to the general population and patients with PV and ET [14]. MF can evolve into acute leukemia in about 10 – 20% of patients [15-17] and while current therapies such as JAK2 inhibitors can improve symptoms and have a modest survival benefit [18-21], the only curative treatment remains allogeneic stem cell transplantation.

